#### 6.3.2. Modified-Intention-To-Treat (mITT) Immunogenicity Population

The modified-intention-to-treat (mITT) immunogenicity population includes all eligible participants who received at least one dose of study product and contributed both pre- and at least one post-vaccination samples for immunogenicity testing for which valid results were reported.

#### 6.3.3. Per Protocol (PP) Immunogenicity Population

The per protocol (PP) immunogenicity population includes all participants in the mITT subset with the following exclusions:

- Data from all available visits for participants found to be ineligible at baseline
- Data from all visits subsequent to major protocol deviations, such as:
  - Second or third vaccination not received
  - Second or third vaccination received out of window
  - Receipt of non-study vaccines during the timeframe prohibited by the protocol
- Data from any visit that occurs substantially out of window

## 6.4. Covariates and Subgroups

The protocol did not define any formal subgroup analyses, and the study is not adequately powered to perform subgroup analyses.

## 6.5. Missing Data

All attempts were made to collect all data per protocol. No imputation will be performed for missing values. Any data point that appears to be erroneous or inexplicable based on clinical judgment will be investigated as a possible outlier. If data points are identified as outliers, sensitivity analyses will be performed to examine the impact of including or excluding the outliers. Any substantive differences in these analyses will be reported.

## 6.6. Interim Analyses and Data Monitoring

### 6.6.1. Safety Review

There was no formal statistical interim analysis based on the safety data. Prior to dose escalation, safety data through 7 days post vaccination of the third dose was reviewed by the principal investigator (PI), MM, and DMID Independent Safety Monitor (ISM). A local DSMB reviewed safety data and provided a recommendation with enrollment and vaccination of the next successive dosage and route of administration cohort. The DMID DSMB was notified when the decision was made to progress to the next cohort. A meeting of the DMID DSMB was planned between Cohort F and Cohort G, but not held because the study was terminated after Cohort E.

### 6.6.2. Immunogenicity Review

The immunology data was not a required element of the data for the DMID DSMB or local DSMB to review. There was no formal statistical interim analysis based on the immunology data planned or performed.

### 6.6.3. Dose Escalation Halting Criteria

Prior to dose escalation to the next cohort within a route of administration group (see [Table 1](#)), safety data through 7 days post vaccination of the third dose was reviewed. Specifically, the SDCC provided the cumulative safety data and notified the PI, MM, and DMID (ISM), that the following criteria had not been met based on a review of the safety data collected in the seven days after the third vaccination of the last participant in the current cohort. Only one cohort was enrolled at a time, and enrollment proceed from Cohort A to B; Cohort C to D, and Cohort E if the halting criteria described below are NOT met.

In addition, there would have been no progression to the next cohort within a route of administration group if the following dose escalation halting criteria had been met:

- The site PI, protocol PI, MM, DMID ISM or local DSMB identify a safety concern that would prompt a review by the DMID DSMB.

If the above dose escalation halting criteria were NOT met, the dose escalation proceed to the next successive route of administration cohort.

If any of the above dose escalation halting criteria had been met, then escalation to the next successive route of administration cohort would not have proceeded and the data would have been reviewed by the DMID DSMB.

### 6.6.3. Halting Rules

Further dosing of any participant only for the route (oral, SL, ID) would have been halted if any of the following criteria were met. The study would have been halted, and all further vaccine administration halted for DSMB review/recommendation if any of the following criteria had been met for each route of administration:

- Any participant experiences vaccine-related SAE (e.g., excluding trauma or accident) from the time of the first study vaccination through the participant's last study visit.
- Any participant experiences an injection site necrosis within 7 days of vaccination.
- Any participant experiences an anaphylactic reaction related to vaccine occurring within 24 hours after vaccination.
- Any participant experiences urticaria, laryngospasm, bronchospasm, or anaphylaxis determined to be related to vaccine and within 7 days of vaccination.
- Any participant experiences facial nerve neuropathy, within 28 days of vaccination, confirmed by an investigator and determined to be related to vaccine.
- Any participant experiences a death for any reason excluding trauma or accident.

In addition, the study would have been halted if two or more participants in the same cohort or three participants across all cohorts within a route of administration (who received at least one dose of study product) experienced:

- The same severe (Grade 3) study vaccine-related local solicited event,
- The same severe (Grade 3) study vaccine-related systemic solicited event,
- The same severe (Grade 3) study vaccine-related clinical laboratory test,
- The same severe (Grade 3) study vaccine-related vital sign, or
- Any other severe (Grade 3) AE of the same system organ class

Exceptions to this would have been:

- If there are obvious and acceptable physiological explanation for a Grade 3 abnormality (example, grade 3 hematuria in menstruating females)

If a halting rule had been met, further dosing of the respective route would have ceased, but follow-up visits would have continued. An *ad hoc* DMID DSMB meeting and local DSMB meeting would have been convened to discuss the halting event. If, following review by both the DMID DSMB and local DSMB, it had been deemed acceptable to restart the study, the study would have resumed, upon DMID's approval and authorization.

### 6.7. Multicenter Studies

Not applicable. This study took place at a single site.

## **6.8.     Multiple Comparisons/Multiplicity**

This study was not designed to test any specific null hypothesis, and as such no adjustments for multiple testing are planned.

## 7. STUDY SUBJECTS

### 7.1. Disposition of Subjects

[Table 16](#) will present a summary of the reasons that participants were screened but not enrolled.

The composition of analysis populations, including reasons for participant exclusion, by treatment arm, is presented in [Table 12](#) and [Table 13](#).

The disposition of participants in the study will be tabulated by treatment group ([Table 10](#) and [Table 11](#)). The table shows the total number of participants screened, enrolled, receiving at least 1 dose, receiving at least 2 doses, receiving all 3 doses, discontinued dosing or terminated from study follow-up and the number completing the study.

A flowchart showing the disposition of study participants, adapted from the Consort Statement [\[5\]](#) will be included ([Figure 1](#), [Figure 2](#), and [Figure 3](#)). This figure will present the number of participants screened, enrolled, lost to follow-up, and analyzed, by treatment arm.

A listing of participants who discontinued dosing or terminated from study follow-up and the reason will be included in [Listing 1](#).

### 7.2. Protocol Deviations

A summary of participant-specific protocol deviations will be presented by the reason for the deviation, the deviation category, and treatment group for all participants ([Table 5](#) and [Table 6](#)). Deviations that are considered major deviations that will be reviewed for possible participant exclusion from the per protocol population include: second or third vaccination not received or received out of window and receipt of non-study vaccines during the timeframe prohibited by the protocol. All participant-specific protocol deviations and non-participant specific protocol deviations will be included in as data listings ([Listing 2](#) and [Listing 3](#), respectively).

## 8. IMMUNOGENICITY EVALUATION

Immune responses will be summarized at each time point within each route by treatment, pooling participants who received placebo. The number and percentage of participants with responses, as defined for each outcome measure in Section 3.3, will be presented.

All immunogenicity variables will be listed by treatment group, participant, and visit (Listing 7, Listing 8, Listing 9, Listing 10, Listing 11, Listing 12, Listing 13, Listing 14, and Listing 15). N, Geometric or Arithmetic Mean, Standard Deviation, Minimum and Maximum will summarize continuous immunogenicity variables, whereas number and percent will summarize categorical immunogenicity variables. Measurements that are titers or concentrations will be summarized by geometric means and 95% confidence intervals (CI). This study was not designed to test a specific null hypothesis, rather the study is designed to assess the safety and immune responses of a range of doses of dmLT when administered by the oral, SL, or ID route in participants residing in an endemic country for ETEC disease.

Immunogenicity data summaries and analysis will be presented for the mITT and PP populations.

### 8.1. Primary Immunogenicity Analysis

Not applicable.

### 8.2. Secondary Immunogenicity Analyses

#### Serum dmLT-specific IgA by ELISA

The number and percentage of participants showing  $\geq 4$ -fold rise from the baseline in serum dmLT-specific IgA concentration determined by ELISA will be presented with exact (Clopper-Pearson) two-sided 95% CI by treatment arm at Days 8, 15, 22, 29, 36, 57, 114, and any time post first dose for Oral and Sublingual Cohorts and at Days 8, 22, 29, 43, 50, 71, 128, and any time post first dose for Intradermal Cohorts (Table 43 and Table 44). Box and whisker plots of fold-rise over time will be presented (Figure 58, Figure 59, Figure 60, Figure 61, Figure 62, and Figure 63).

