8.2.3 Special Assays or Procedures

Detailed procedures for the conduct of each of the immunology assays are described in the *Manual of Procedures*.

The following immunology assays will be performed at icddr,b (Dhaka, Bangladesh):

Table 3: Assays to be performed at icddr,b

Immunology Assay:	Visit(s) collected at:
Serum anti-dmLT IgG and IgA by ELISA	Visits 1, 2, 3, 4, 5, 6, 7, and 8
dmLT-specific IgG and IgA ASC assays	Visits 1, 2, 3, 4, 5, and 6
dmLT-specific IgG and IgA ALS assays	Visits 1, 2, 3, 4, 5, and 6
ASC homing studies	Visits 2, 4, and 6
Fecal total IgA and anti-dmLT IgA by ELISA	Visits 1, 2, 3, 4, 5, 6 and 7
Saliva total IgA and anti-dmLT IgA by ELISA	Visits 1, 2, 3, 4, 5, 6 and 7
dmLT-specific memory B cell responses	Visits 1, 4, 6, 7, 8, and 9

The following immunology assay will be performed at CVD (Baltimore, MD, U.S.):

- Serum toxin (LT) neutralization assay
- dmLT-specific effector and memory T cell responses, by CyTOF--including the characterization of: homing potential, cytokine/chemokine production profile, degranulation capacity, and activation potential
 - Collected at visits screening, 4, 6, 7, 8, and 9

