### dmLT-specific effector and memory T cell responses by CyTOF

The number and percentage of participants with dmLT-specific effector and memory T cell responses as measured by CyTOF will be presented with exact (Clopper-Pearson) two-sided 95% CI by treatment arm at Days 22, 36, 57, 114, 209, and any time post first dose for Oral and Sublingual Cohorts and at Days 29, 50, 71, 128, 223, and any time post first dose for Intradermal Cohorts ([Table 73](#) and [Table 74](#)). Box and whisker plots of % ratio to baseline over time (beginning at [Figure 112](#) and concluding with [Figure 237](#)) will be presented.

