### Comparison of Immunogenicity Responses

Spearman rank correlations with 95% CI for peak immunogenicity responses will be presented by Cohort (beginning at [Table 75](#) and concluding with [Table 90](#)).

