## 9.7. Vital Signs and Physical Evaluations

The baseline value will be defined as the last value obtained prior to the first vaccination/dose of study product. If a participant has repeated vital sign measurements on the same day, the value from the last evaluation will be used for analysis. Post-baseline, in the case of multiple observations (for example, from supplemental visits), the assessment value that is closest to the scheduled visit window will be used in the analyses. All the recorded data will be listed. If observations have the same distance to the scheduled assessment, the latest one will be used.

Vital sign measurements include systolic blood pressure, diastolic blood pressure, pulse, and oral temperature. Grading scales for vital signs are presented in [Table 9](#). Vital signs were assessed at Day 1, Day 8, Day 15, Day 22, Day 29, Day 36, Day 57, Day 114 and Day 209 for Oral and Sublingual Cohorts and at Day 1, Day 8, Day 22, and Day 29 for Intradermal Cohorts. Vital signs will be tabulated by severity, visit, and treatment group ([Table 160](#), [Table 161](#), [Table 162](#), [Table 163](#), and [Table 164](#); [Listing 25](#)).

Physical Examinations were performed at screening to assess general wellness. The following body systems were assessed: head, eyes, ears, nose, and throat; lymph nodes; skin; pulmonary; cardiovascular; abdominal; neurological; and musculoskeletal systems. At subsequent visits including enrollment a targeted physical examination was conducted if indicated based on review of medical history. Findings will be presented in Listing 26.

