**15. SUMMARY OF CHANGES IN THE CONDUCT OF THE STUDY OR PLANNED ANALYSES****Changes to Study Conduct**

- At the request of the local (icddr,b) DSMB, collection of serum bilirubin at screening and Visit 6 and collection of ALT and creatinine at Visit 6 were added to the safety labs. These results were not obtained for Cohorts A through C which were enrolled prior to the request.
- Due to a country-wide lockdown instituted in Bangladesh to combat the COVID-19 pandemic all Cohort E participants did not receive a third dose of study product. Cohort D participant Visits 8 and 9 and Cohort E participant Visits 6 through 9 were not conducted and no further cohorts were enrolled due to the pandemic.

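### After the shutdown, the any-time responder and GMFR rows cover fewer visits in Cohort E (all assays) and Cohort D (serum, neutralization, memory B and T cells), so those contrasts need a common window

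*SAP*

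**What the plan says.** The secondary responder endpoints in SAP 3.2.2 count a participant who responds at any point after vaccination. For serum, SAP 8.2 gives a responder rate on each of seven post-dose days (Day 8 to Day 114) and one at "any time post first dose for Oral and Sublingual Cohorts". The intradermal cohort has its own seven days, running from Day 8 to Day 128, and the same closing row. Protocol 8.2.3 (Table 3) gives the serum collection points as "Visits 1, 2, 3, 4, 5, 6, 7, and 8", the first being baseline. For T cells, SAP 8.3 uses "Days 22, 36, 57, 114, 209, and any time post first dose" in the oral and sublingual cohorts. The serum, neutralization, ALS, fecal and salivary shells also carry a GMFR in the any-time row.

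These lists are the schedule as planned. SAP Section 15 records that "Cohort D participant Visits 8 and 9 and Cohort E participant Visits 6 through 9 were not conducted" and that no Cohort E participant received a third dose. Section 9.7 gives vital signs at "Day 1, Day 8, Day 22, and Day 29 for Intradermal Cohorts", which implies that Cohort E's Visit 5 (Day 43) was not held either, although Section 15 does not list it. Section 6.5 rules out imputation. No section sets a common window for the any-time rows.

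**The concern.** A maximum, or the chance of crossing a threshold at least once, cannot fall when visits are added. Cohorts seen more often therefore have an advantage in the any-time row even if the product does the same in each. The protocol's background (Section 2.1) asks whether responses differ by route, and readers will take side-by-side columns as an answer.

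The SAP made the corresponding adjustment elsewhere. The vital-sign shells (Tables 160-164) drop Cohort D after Day 57 and Cohort E after Day 29, and use a Cohort C placebo column at the late visits. The 7-day post-dose-3 chemistry rows show only Cohort D and its own placebo. The immunogenicity shells keep every cohort and the pooled sublingual placebo in one any-time row, with no count of contributing visits.

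**Working it through.** **Planned counts.** SAP 8.2 lists 7 post-dose serum days for oral/sublingual and 7 for intradermal. Protocol Table 3 gives Visits 2-8, also 7. Memory B and T cells are collected after dosing at Visits 4, 6, 7, 8 and 9, which is 5. The plan's own counts reproduce.

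**Counts after the shutdown.** Remove Visits 8-9 for D, Visits 6-9 for E, and Visit 5 for E if Section 9.7 is followed.

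| Assay (post-dose visits) | A-C | D | E |
|---|---|---|---|
| Serum IgA/IgG, neutralization (2-8) | 7 | 6 | 3 (4 if Visit 5 held) |
| ASC, ALS (2-6) | 5 | 5 | 3 (4) |
| Fecal, salivary IgA (2-7) | 6 | 6 | 3 (4) |
| ASC homing (2, 4, 6) | 3 | 3 | 2 |
| Memory B, T cells (4, 6, 7, 8, 9) | 5 | 3 | 1 |

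Every contrast with E is unequal. A-C against D is unequal in the first and last rows only. A vs B, A vs C and B vs C are equal throughout. The pooled sublingual placebo mixes the C and D windows in the first and last rows.

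**Possible size.** Assume no vaccine effect and independent normal errors with within-person SD s at baseline and at each of k post-dose visits. The chance of at least one rise beyond threshold c is 1 - ∫ φ(b) Φ(b + c/s)^k db. For a 4-fold rise c = log2(4) = 2; for the T cell rule c = 0.05 percentage points. As s grows the limit is k/(k+1). The documents give no value for s, so a range is shown. Figures are from 400,000 simulated draws; numerical integration of the formula agrees to about 0.1 of a point.

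| Serum 4-fold, log2 SD | 7 visits | 6 visits | 3 visits |
|---|---|---|---|
| 0.5 | about 1% | about 1% | about 1% |
| 0.75 | 13.2% | 11.9% | 7.3% |
| 1.0 | 28.9% | 26.7% | 17.7% |

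| T cell rule, SD (percentage points) | 5 visits | 3 visits | 1 visit |
|---|---|---|---|
| 0.01 | about 0.1% or less | about 0.1% or less | about 0.1% or less |
| 0.02 | 13% | 9% | 4% |
| 0.05 | 55% | 45% | 24% |
| 0.5 | 81% | 72% | 47% |

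If Cohort E's Visit 5 was held, its serum rates become about 9% (SD 0.75) or 21% (SD 1.0).

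**Scale.** SAP 4.4.3 plans 12 vaccinees per cohort, so one person is 1/12 = 8.3 points. The serum gap between 7 and 6 visits is 13.2 - 11.9 = 1.3 or 28.9 - 26.7 = 2.2 points, well under one person. The gap between 7 and 3 visits is 5.9 or 11.2 points.

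**The case against.** The analysis is descriptive. SAP 6.8 tests no hypothesis, Section 4.2 says placebo recipients are there for blinding and not for comparison, Section 8 summarizes by time point within route, and the lost visits are disclosed. The by-visit rows already allow a matched reading, and response at any time is the protocol's own endpoint. All of this is correct and limits the consequence. It does not remove the problem: the any-time row is the stated secondary endpoint, and it is the row that is not matched.

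A reader might infer that every dose and route comparison is biased, or that sublingual 25 µg will look worse on the secondary endpoints generally. The visit counts do not support either. ASC, ALS, fecal and salivary windows are the same in A-D, and the secondary serum endpoints differ by a single late visit. The large illustrated gaps belong to T cells, which are exploratory, and they vanish at small assay noise.

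A reader might also put a lower Cohort E rate down to fewer visits alone. Cohort E received two of three doses, so a shorter regimen is an equally available explanation.

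Nor are the peak correlations a cross-cohort comparison: "Spearman rank correlations with 95% CI for peak immunogenicity responses will be presented by Cohort". Within a cohort everyone has the same schedule. Only the pooled sublingual placebo column is mixed, and only where serum is one of the pair. Memory B and T cells do not enter those tables.

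**Conclusion.** The point holds in limited form. The any-time responder rows, and the GMFR rows where present, cover unequal windows for any contrast with Cohort E, and for A-C against D in serum IgA/IgG, neutralization, memory B and T cells. The direction is certain, because extra visits cannot lower a maximum. The size is not known: it rests on within-person variability that the documents do not give and on an assumption of independent errors, and it would be zero if nobody first responded at a later visit. For serum in A-C against D it is about 0 to 2 points under these assumptions. It could be material for T cells and for contrasts with E, where it is also mixed with the missing third dose. The 3 visits for E rest on Section 9.7; Section 15 read literally allows 4 for the assays collected at Visit 5, and the two sections should be reconciled. This is worth changing because the change is cheap, not because the planned analysis is invalid.

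**What to change.** 1. Add an any-time row through 7 days post-dose 2 (Day 22 oral/sublingual, Day 29 intradermal) for A-E in the serum, neutralization, ASC, ALS, homing, fecal and salivary tables. Every cohort then has two doses and the same visits: 2-4, or 2 and 4 for homing. This row does not depend on whether Visit 5 was held. For memory B and T cells the existing post-dose 2 Day 7 row already does this.
2. Add an any-time row through Day 57 for A-D for serum, neutralization, memory B and T cells only. For the other assays it would repeat the existing row.
3. On the full-window row, show the contributing visits for each cohort, and base cross-cohort statements on the common-window rows.
4. Footnote the correlation tables with the visits used and, where serum is involved, note the mixed sublingual placebo column.
5. Reconcile Sections 9.7 and 15 on Cohort E's Visit 5.

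No new data are needed. The cost is extra table rows. The largest share is in the T cell tables, which have 42 marker panels (126 figures at three per marker) in each of two populations. Common-window rates omit late responses, which is why the full-window row should stay.

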#### Serum dmLT-specific IgG by ELISA

The number and percentage of participants showing  $\geq 4$ -fold rise from the baseline in serum dmLT-specific IgG concentration determined by ELISA will be presented with exact (Clopper-Pearson) two-sided 95% CI by treatment arm at Days 8, 15, 22, 29, 36, 57, 114, and any time post first dose for Oral and Sublingual Cohorts and at Days 8, 22, 29, 43, 50, 71, 128, and any time post first dose for Intradermal Cohorts (Table 45 and Table 46). Box and whisker plots of fold-rise over time will be presented (Figure 64 Figure 65 Figure 66 Figure 67 Figure 68 , and Figure 69).

#### dmLT-specific IgA ASC by ELISpot

The number and percentage of participants showing with  $\geq 8$  dmLT-specific IgA ASC /  $10^6$  PBMC as measured by ELISpot will be presented with exact (Clopper-Pearson) two-sided 95% CI by treatment arm at Days 1, 8, 15, 22, 29, 36, and any time for Oral and Sublingual Cohorts and at Days 1, 8, 22, 29, 43, 50, and any time for Intradermal Cohorts (Table 49 and Table 50).

